6.6. Longitudinal Assessments

To compare disease progression as measured by VTC versus on-site, an MMRM will be fit to the clinical assessment measures. Observations will be grouped by test modality (VTC and on-site). The MMRM will include terms for modality, visit, visit-by-modality interaction, age, years of education, and presence/absence of anti-dementia drugs. Visit will be considered a categorical variable. The null hypothesis is that the contrast between the VTC modality versus the on-site modality at each visit equals 0. An unstructured covariance matrix will be used to model the within-subject variance-covariance errors. If the unstructured covariance structure matrix results in a lack of convergence, the following tests will be used in sequence:

- heterogeneous Toeplitz covariance structure
- heterogeneous autoregressive covariance structure
- heterogeneous compound symmetry covariance structure
- compound symmetry covariance structure

The Kenward-Roger approximation will be used to estimate the denominator degrees of freedom.

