### 9.2. Sample Size Determination

Approximately 200 participants will be enrolled and randomized in a 1:1 ratio to the 2 groups (Group 1: Cognitive/functional scale assessment on-site, followed by VTC assessment; or Group 2: Cognitive/functional scale assessment by VTC, followed by assessment on-site). It is expected that approximately 180 participants will complete Pair 1 of Part A. Approximately 150 participants are expected to complete the study.

A correlation coefficient of 0.80 between on-site and VTC assessment is assumed.

Furthermore, it is assumed that the 2 modalities will yield similar means but different standard deviations. A mean ADAS-Cog13 total score of 27.2 and a SD of 8 and 9 were used for the power calculation. These estimates were derived from Studies I8D-MC-AZES, I8D-MC-AZET, and H8A-MC-LZAX, all reflecting an early or mild AD population.

This sample size will provide approximately 81% power to demonstrate 'acceptable' reliability, defined as the lower limit of the 95% confidence interval for ICC above 0.70.

This power calculation is based on the ADAS-Cog13, as this is the scale anticipated to have most scale adaptations and most variability from on-site to VTC assessment. Other scales should therefore demonstrate equal or greater power for these comparisons.

Simulations (carried out in R) with 1000 iterations, utilizing above described assumption, yields an average ICC of 0.793 and average 95% confidence interval of 0.732 to 0.841.

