### 9.4.4. Tertiary/Exploratory Endpoint(s)

As a sensitivity analysis for the primary endpoint of Part A, to assess whether the VTC clinical assessment includes any bias relative to the on-site clinical assessment, an ICC looking at the consistency of the 2 measures will be calculated – ICC(C,1) per McGraw and Wong (1996). By definition, the consistency ICC will be equal to or larger than the ICC for absolute agreement. Large differences between the absolute agreement and consistency ICCs suggest a shift (upward or downward) in the VTC relative to the on-site assessment.

Using the same ANOVA model specified in Section 9.4.2, the ICCs and 95% confidence intervals for the second pair and third pair of on-site and remote clinical assessments will be estimated. Comparisons between the ICCs from the first pair of assessments and the second and third pairs of assessments will be made to measure consistency across measures. If fewer than 50 pairs of clinical assessments are collected for Pairs 2 or 3, only descriptive statistics will be reported. See the SAP for further details.

To compare disease progression as measured by VTC versus on-site, an MMRM will be fit to the clinical assessment measures. Observations will be grouped by test modality (VTC and on-site).

The MMRM will include terms for modality, visit, visit-by-modality interaction, age, years of education, and presence/absence of anti-dementia drugs. Visit will be considered a categorical variable. The null hypothesis is that the contrast between the VTC modality versus the on-site modality at each visit equals 0. An unstructured covariance matrix will be used to model the within-subject variance-covariance errors. If the unstructured covariance structure matrix results in a lack of convergence, the following tests will be used in sequence:

- heterogeneous Toeplitz covariance structure
- heterogeneous autoregressive covariance structure
- heterogeneous compound symmetry covariance structure
- compound symmetry covariance structure

The Kenward-Roger approximation will be used to estimate the denominator degrees of freedom.

Changes in the blood-based biomarkers of NfL, P-tau, and A $\beta$  during Part B will be summarized with observed case analyses.

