6.1. General Considerations

Statistical analyses of this study will be the responsibility of the sponsor or its designee.

Unless otherwise noted, statistical tests will be conducted at a 2-sided alpha level of 0.05 and 95% confidence intervals will be displayed as 2-sided.

No adjustments for multiple comparisons are planned.

All analyses involving calculation of ICCs will be limited to the Part A: Video Assessment population, requiring participants to contribute complete pairs of on-site and remote clinical assessments to be included. The ICC will be calculated as 2-way mixed-effect model looking for absolute agreement across raters, with raters defined as on-site assessment and VTC assessment.

A database lock is expected to occur after all randomized participants have completed participation in Part A of the study. Analyses related to the validation of remote assessments compared to on-site assessments will be conducted. As no study drug is administered during Part A, safety analyses will be limited.

Additional exploratory analyses of the data will be conducted as deemed appropriate.

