8.1. General Considerations

Objectives for Part C of AACH will be addressed with summaries of clinical, imaging, and biomarker data. Data collected from the feeder study from which the participant came, and data from the first on-site visit from Part A will be aggregated with data from Part C to allow for display of longitudinal changes. For comparative purposes, subjects that participate in Part B will also be displayed, with their feeder study, first Part A on-site visit, and Visit 1 from Part B (pre-treatment) aggregated in a similar fashion.

Unless otherwise specified, baseline for clinical, imaging, and biomarker endpoints will be defined as the last observation prior to study drug initiation from the feeder study. When change from baseline is assessed, patients will be included in the analysis only if both a baseline and a Part C measure are available.

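### The exploratory Part A MMRM could gain precision cheaply by adjusting for each participant's last originating-study score on the same scale

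*SAP*

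**What the plan says.** SAP 6.6 compares progression by VTC and on-site with an MMRM. Its terms are: "The MMRM will include terms for modality, visit, visit-by-modality interaction, age, years of education, and presence/absence of anti-dementia drugs". Protocol 9.4.4 lists the same terms. Both state the hypothesis in the same way: "The null hypothesis is that the contrast between the VTC modality versus the on-site modality at each visit equals 0". Neither lists a baseline or earlier score on the scale being analysed. Protocol 9.1 expects progression measured by VTC to be no different from progression measured on-site and sets no margin for that comparison.

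No cognitive or functional scale is scheduled at V601 (Protocol 1.3), so a score from before randomisation can come only from the originating study. Every participant must have taken part in one (Protocol 5.1, criterion 1). The SAP uses such data elsewhere. For Part C, SAP 8.1 says "Data collected from the feeder study from which the participant came, and data from the first on-site visit from Part A will be aggregated" with Part C data, and it treats Part B participants in a similar way for comparison. The Part C clinical ANCOVA in SAP 8.6 adjusts for baseline score.

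**The concern.** In a crossover one expects each person to serve as their own control. The contrast at a single visit does not use that feature. Participants alternate modality from a randomised start and are seen by one modality at each visit, so at any given visit order group and modality coincide. With visit-by-modality terms in the model, the VTC-minus-on-site contrast at a visit is a difference between two groups of people and carries the full between-person spread.

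Age, education and drug status are the only adjustments. An earlier score on the same scale would usually predict more, and because it predates randomisation it can be added without introducing bias. It would also remove chance differences in severity between the two order groups. This matters because the protocol expects no difference: with no margin set, a wide and non-significant contrast can be taken as agreement.

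**Working it through.** **Inputs**
- Protocol 9.2: "Approximately 200 participants will be enrolled and randomized in a 1:1 ratio to the 2 groups"; "It is expected that approximately 180 participants will complete Pair 1 of Part A", so about 90 per order group; "A correlation coefficient of 0.80 between on-site and VTC assessment is assumed"; and for ADAS-Cog13 a mean "total score of 27.2 and a SD of 8 and 9 were used for the power calculation".
- SAP 6.1: "statistical tests will be conducted at a 2-sided alpha level of 0.05 and 95% confidence intervals will be displayed as 2-sided".
- Assumed here, because the documents give neither: the correlation rho between the last originating-study score and a Part A score (0.3 to 0.8), and the VTC shift (1 to 3 points).

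**The plan's own figure.** Protocol 9.2 claims about 81% power for the primary ICC criterion, an average ICC of 0.793 and an average interval of 0.732 to 0.841. Simulating bivariate normal scores with mean 27.2, SD 8 and 9, correlation 0.80 and n = 180 gives 82.6% power, a mean ICC of 0.793 and a mean interval of 0.732 to 0.841. The inputs are therefore read as intended. The documents state no power or precision for the MMRM contrast.

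**Planned contrast at one visit, 90 per group**
- SE = sqrt(64/90 + 81/90) = sqrt(145/90) = 1.27 points.
- 95% half-width = 1.96 × 1.27 = 2.49 points.
- Difference detectable with 80% power = 3.56 points.

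A generalised least squares check over six visits with complete data gave 1.27 at every visit, so the unstructured covariance does not sharpen the contrast.

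**With the prior score added.** Adjusted SE = 1.27 × sqrt(1 − rho²). Power is two-sided at 5%, normal approximation.

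| rho | SE | SE cut | 95% half-width | Power, 1 point | Power, 2 points | Power, 3 points |
|---|---|---|---|---|---|---|
| planned | 1.27 | – | 2.49 | 12% | 35% | 66% |
| 0.3 | 1.21 | 5% | 2.37 | 13% | 38% | 70% |
| 0.5 | 1.10 | 13% | 2.15 | 15% | 44% | 78% |
| 0.7 | 0.91 | 29% | 1.78 | 20% | 60% | 91% |
| 0.8 | 0.76 | 40% | 1.49 | 26% | 75% | 98% |

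At rho 0.8 the variance falls by 0.8² = 64%, which is worth 90/0.36 = 250 per group.

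**What shrinks the gain**
- *Attrition.* At rho 0.8, if 60 per group stay for Pair 2 and 40 for Pair 3 (assumed), the SE falls from 1.36 to 0.89 (35%) and from 1.46 to 1.04 (29%). With 25 and then 15 per group (assumed), the cuts are 23% and 17%.
- *Covariates already in the model.* If they explain a share R of both scores, the partial correlation is (rho − R)/(1 − R). For R of 10% and 20% (assumed), the 40% cut at rho 0.8 becomes 37% and 34%. The 13% cut at rho 0.5 becomes 10% and 7%.

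**Within-person comparison.** The Pair 1 difference within participants has SE = sqrt((64 + 81 − 2 × 0.80 × 8 × 9)/180) = sqrt(29.8/180) = 0.41. The prior score adds nothing to it.

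**The case against.** The strongest reply is that little hangs on this model. It sits under the tertiary and exploratory endpoints. The Part A primary is the Pair 1 ICC, the sample size was set for that alone, and leaving a prognostic covariate out of a randomised comparison does not bias it. A systematic VTC shift also has a planned check of its own, the comparison of the consistency ICC with the absolute-agreement ICC. All of this stands. The point concerns efficiency; the plan contains no error here.

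The next reply is that the imprecision comes from the choice of contrast, and that a within-person comparison (SE 0.41) beats the adjusted one even at rho 0.8 (SE 0.76). That is correct for a Pair 1 modality difference. The hypothesis as written is nevertheless stated visit by visit, and for that contrast the covariate helps.

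Third, the response is ambiguous. The endpoint table in Protocol 3 speaks of change from V602, whereas SAP 6.6 fits the measures themselves. If change from V602 is modelled, the originating-study score adds little. This stands and has to be settled first.

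A reader might also infer two stronger claims:
- *A real VTC shift would usually be missed.* The planned model has 66% power for a 3-point shift. The claim fits only shifts of about 1 to 2 points, and the documents state no expected shift.
- *Every visit contrast is far less precise than it need be.* The 0.80 in Protocol 9.2 is the correlation between on-site and VTC scores, not between the originating study and Part A. The gap to V602 has a 30-day minimum and no stated maximum, so rho could be low. Pairs 2 and 3 are optional, and SAP 6.5 itself expects that numbers there may be limited.

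**Conclusion.** This is a cheap improvement to an exploratory analysis. The omission is confirmed in both documents, and the contrast as written is between order groups, with SE 1.27 and a half-width of 2.49 ADAS-Cog13 points in Pair 1. Adjusting for the last originating-study score would lower that SE by about 5% to 40% for rho from 0.3 to 0.8.

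The figures rest on the Protocol 9.2 SDs, about 90 per group, the score at each visit as the response, an assumed rho and an assumed shift. They apply to ADAS-Cog13; the documents give no SDs for the other scales. The gain is smaller in later pairs if few participants continue, and smaller to the extent that the existing covariates already explain variance. The documents do not support reading this as a threat to the primary ICC result or as a bias in the MMRM.

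**What to change.** In SAP 6.6 and Protocol 9.4.4:
- state that the response is the score at each visit;
- add the last originating-study score on the same scale before Part A randomisation, and its interaction with visit;
- report each VTC-minus-on-site contrast with its 95% confidence interval;
- keep participants who have no such score by mean imputation of the covariate plus a missing-value indicator. SAP 6.3 rules out imputation in Part A efficacy analyses, so the text should say that this applies to the covariate only and that no outcome is imputed.

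Do not add the covariate to the primary ICC model, where it would remove true between-person variance from the quantity being estimated.

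The cost is a short text change and some data work, with no added visits or participants. The linkage in SAP 8.1 covers Part C and Part B participants, so it must be extended to those who do Part A only and be ready for the Part A database lock. The sponsor must also confirm that every originating study collected each scale. SAP 8.6 names ADCS-iADL, whereas the Part A measure is the ADCS-ADL total.

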To assess long-term effect of donanemab on brain amyloid deposition, brain tau deposition, blood-based biomarkers, and clinical progression of AD in participants who received donanemab in the originating study	Change in the following endpoints from baseline in the originating study through $\geq 52$ weeks after the participant's last double-blind visit in the originating study, using Part C assessments: 
 
• Amyloid plaque deposition as measured by florbetapir F 18 PET scan
 
• Tau deposition as measured by flortaucipir F 18 PET scan
 
• NfL
 
• P-tau
 
• A<math>\beta</math>
 
• MMSE score
 
• ADAS-Cog13 score
 
• iADRS score
 
• ADCS-iADL score
 
• CDR-SB
 

To assess the effect of donanemab on blood-based biomarkers	Change from baseline to Week 72 in the following blood-based biomarkers in Part B: 
 
• NfL
 
• P-tau
 
• A<math>\beta</math>
 

To evaluate the reliability of VTC compared with on-site administered cognitive and functional measures	
The intraclass correlation between VTC and on-site assessment for PAIR 2 and PAIR 3 compared with intraclass correlation of PAIR 1 for
 
 
• ADAS-Cog13
 
• ADCS-ADL
 
• MMSE
 
• CDR-SB
 

To assess clinical progression as measured by VTC versus F2F-administered cognitive and functional measures	
Change from V602 to V608 as measured by
 
 
• ADAS-Cog13
 
• ADCS-ADL
 
• MMSE
 
• CDR-SB
 

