#### **4.1.2. Part A: Video Assessment**

Part A is a multicenter, randomized, multiple crossover study to validate remote assessment of cognitive and functional scales. Part A begins at Visit 601 (randomization), after screening is complete. Participants are randomized to one of 2 groups, as described in the Schema and Overall Design (Sections 1.2 and 4.1, respectively) to be assessed both remotely (through VTC) as well as on-site.

Part A consists of 6 assessments or 3 pairs:

- Pair 1 comprises Visits 602 and 603
- Pair 2 comprises Visits 604 and 605
- Pair 3 comprises Visits 606 and 607

In each pair, each participant is assessed once remotely through VTC and once in person on-site. The participant may elect to proceed to Part B (Visit 1) at any time after participating in Part A Pair 1.

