## **6.3. Measures to Minimize Bias: Randomization and Blinding**

### **Part A**

For the video assessment period, participants will be randomized 1:1 to either

- Group 1: Cognitive/functional scale assessment performed on-site, followed by at-home (VTC) assessment, or
- Group 2: Cognitive/functional scale assessment at home (VTC), followed by on-site assessment.

To minimize bias, participants follow a crossover design, alternating between assessment locations, starting with their randomized initial location.

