## 9. Statistical Considerations

### 9.1. Statistical Hypotheses

#### Part A:

The ICC comparing VTC administration of the ADAS-Cog13, the ADCS-ADL, the MMSE, and the CDR-SB will show at a minimum 'acceptable' agreement with the on-site assessment of the same scales. Acceptable agreement is defined as an ICC value of 0.70 or greater (Koo and Li 2016; Coons 2009).

The ICC will remain consistent across multiple pairs of VTC and on-site assessments.

Disease progression measured by VTC administration will be no different than disease progression measured by on-site assessments.

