6.5. Primary Objective

The primary objective of Part A of this study is to evaluate the reliability of VTC compared with on-site administered cognitive and functional measures. This will be assessed by estimating the intra-class correlation (ICC) and the associated 95% confidence interval for the first pair of

observations from participants and comparing the lower bound of the confidence interval to 0.70, the ICC cut-off for acceptable reliability.

Using the guidelines and notation for defining ICCs published by McGraw and Wong (1996), the ICC of primary interest for this study is a 2-way mixed model, interaction absent, with single measurements from each modality on participants, looking at absolute agreement – ICC(A,1). In the present study, the ‘raters’ are the two modalities by which the clinical scales are assessed, on-site and VTC. As we are interested in comparing these specific modalities, modality is considered a fixed effect.

For ADAS-Cog₁₃ total score, ADCS-ADL total score, iADRS total score, CDR Sum of Boxes, and MMSE total score, individual mixed models will be fit to the data with fixed effects of modality, time effect, age, years of education, and presence/absence of anti-dementia drugs and a random effect for subject. ICCs will be estimated using the mean squares from these models and defined as:

Absolute Agreement: $ICC (A,1) = (MS_{subj} - MS_{error}) / (MS_{subj} + MS_{error} + 1/n(MS_{modality} - MS_{error}))$

Consistency: $ICC (C,1) = (MS_{subj} - MS_{error}) / (MS_{subj} + MS_{error})$

95% Confidence intervals for these quantities will be constructed as specified in Table 7 of McGraw and Wong (1996).

Similar analyses will also be conducted for pairs 2 and 3 of each of the clinical outcomes specified above. As the number of subjects contributing additional pairs may be limited, no specific hypothesis/test is specified.

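### SAP 6.6 sets out to compare progression by video and on-site assessment, but its stated null tests level at each visit; no change contrast or margin is named

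*SAP*

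**What the plan says.** - **Aim (SAP 6.6):** "To compare disease progression as measured by VTC versus on-site, an MMRM will be fit to the clinical assessment measures".
- **Model (SAP 6.6):** "The MMRM will include terms for modality, visit, visit-by-modality interaction, age, years of education, and presence/absence of anti-dementia drugs". Visit is categorical, observations are grouped by modality, and the within-subject covariance is unstructured with listed fallbacks.
- **Test (SAP 6.6):** "The null hypothesis is that the contrast between the VTC modality versus the on-site modality at each visit equals 0". Protocol 9.4.4 has the same model and null.
- **Hypothesis (Protocol 9.1):** "Disease progression measured by VTC administration will be no different than disease progression measured by on-site assessments".
- **Endpoint (Protocol 3, exploratory):** "Change from V602 to V608 as measured by" ADAS-Cog13, ADCS-ADL, MMSE and CDR-SB.
- **Design:** Part A has six assessments in three pairs (Protocol 4.1.2), and the last is defined by "Pair 3 comprises Visits 606 and 607". Participants keep "alternating between assessment locations, starting with their randomized initial location" (Protocol 6.3).
- **Later pairs (SAP 6.5):** "As the number of subjects contributing additional pairs may be limited, no specific hypothesis/test is specified".

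**The concern.** The aim, the hypothesis and the endpoint all concern change over time. The stated null concerns level. If VTC scores sit a fixed amount above on-site scores and both decline at the same rate, progression is identical and the null is false. If the two modalities diverge but cross, the level difference can be near zero at several visits while progression differs. Neither document names a change contrast or a test of the visit-by-modality term.

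Three further gaps follow.

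- **Visit is not defined.** It could mean V602 to V607 or pair number, and this decides whether a contrast compares different people or the same people.
- **There is no decision rule.** A test against zero with no margin cannot support a claim of no difference. The 0.70 cut-off belongs to the ICC.
- **The endpoint cannot be computed.** It ends at a visit outside the schedule.

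This is the only planned analysis of the progression question in Part A. As written, the contrast that answers it would be chosen after the data are seen.

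**Working it through.** **Inputs.** Protocol 9.2: ADAS-Cog13 mean 27.2, SDs 8 and 9, correlation 0.80 between modalities, about 180 completers of Pair 1, 1:1 allocation (90 per group). SAP 6.1: two-sided alpha 0.05. Covariates are ignored and data are complete.

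**The plan's own figure.** No power or precision is given for this analysis. The only power figure is for the ICC: about 81%, mean ICC 0.793, mean 95% CI 0.732 to 0.841. Simulation with these inputs gives 0.793, 0.732 to 0.841 and 83% power; a Fisher-z approximation gives 80.9%. The inputs are therefore being used as the plan uses them.

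**1. Who is compared if visit means V602 to V607**

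| | V602 | V603 | V604 | V605 | V606 | V607 |
|---|---|---|---|---|---|---|
| Group 1 | on-site | VTC | on-site | VTC | on-site | VTC |
| Group 2 | VTC | on-site | VTC | on-site | VTC | on-site |

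At every visit one group is the whole VTC cell and the other the whole on-site cell. The visit-by-modality model, fitted by generalised least squares with unstructured covariance to simulated complete data, gave six contrasts equal to the raw group differences to four decimals.

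**2. Precision for a level difference.** Variances are 64 and 81; the covariance is 0.8 × 8 × 9 = 57.6.

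- Per-visit contrast: √(64/90 + 81/90) = 1.269, 95% CI ±2.49.
- Within-person Pair 1 difference: √((64 + 81 − 115.2)/180) = 0.407, 95% CI ±0.80. The average of the V602 and V603 contrasts has this same SE.
- Power for a 2-point shift (size chosen for illustration): 35% against over 99%.
- Pair-number reading, if the two records at each level were treated as independent: √(145/180) = 0.898.

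**3. Sign changes.** The groups swap modality at each visit, so adjacent contrasts correlate at −115.2/145 = −0.794. In 40,000 simulated trials the V602 and V603 contrasts had opposite signs in 79% with no modality effect and in 43% with a true 1-point VTC shift.

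**4. Level is not progression.** Simulated rejection rates, 180 participants completing all six visits; offsets and slopes are assumed.

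| Scenario | Each per-visit test | At least one of six | Change contrast (step 5) |
|---|---|---|---|
| VTC 2 points higher throughout, same progression | 34–35% | 90% | 5% |
| VTC starts 1 point higher and stays flat; on-site rises 0.5 per visit | 5–22% | 39% | 94% |

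**5. The contrast that answers the aim.** For each person take (VTC Pair 3 − VTC Pair 1) − (on-site Pair 3 − on-site Pair 1), averaged over the two groups. With every between-visit covariance equal to 57.6, its variance is 2(81 − 57.6) + 2(64 − 57.6) = 59.6.

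- 180 completing three pairs: √(59.6/180) = 0.575, 95% CI ±1.1.
- 60 completing three pairs: √(59.6/60) = 0.997, 95% CI ±2.0.

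Both counts are assumed. The plan gives no same-modality retest correlation r. With r in its place, the variance is 2(1 − r) × 145:

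| r (assumed) | SE, n = 180 | SE, n = 60 |
|---|---|---|
| 0.80 | 0.568 | 0.983 |
| 0.85 | 0.492 | 0.851 |
| 0.90 | 0.401 | 0.695 |

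**6. The endpoint.** V608 is not in the Schedule of Activities or the pair definitions. Ending at V607 does not repair it: by the table in step 1, nobody has the same modality at V602 and V607. The longest same-modality spans are V602 to V606 and V603 to V607.

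**The case against.** - **The model already holds the answer.** It contains visit-by-modality, and if every per-visit null were true the two trajectories would coincide. Both statements are correct. But the converse fails, no joint test is stated, and a constant offset breaks every per-visit null without any difference in progression.
- **Visit may mean pair number.** The sentence on grouping observations by modality fits that reading. Each contrast is then within-person, and the Group 1 against Group 2 point falls away. The level-versus-change point does not. The SE of 0.90 illustrates one way of handling two records per level; the text does not specify any.
- **The response may be change from V602.** Protocol 3 hints at this, but SAP 6.6 fits the measures themselves. Even on that reading, alternation makes only V604 and V606 same-modality changes from V602.
- **The per-visit comparison is randomised.** This stands: it is unbiased, and the fault is a wrong target and low precision. Exact equality with the group difference also needs complete data, which is not expected after Pair 1.
- **The within-person level difference is largely available already.** SAP 6.5 fits modality as a fixed effect for Pair 1, with similar analyses for Pairs 2 and 3, and the gap between ICC(A,1) and ICC(C,1) shows a shift. This stands in part, but reporting of the modality estimate itself is not promised.
- **Most of the precision figures concern level.** This stands. Those for progression rest on assumed later-pair numbers and correlations.
- **The objective is exploratory.** This stands and limits how much turns on the point.

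**Conclusion.** The concern holds. Under either reading of visit, the stated null addresses level while the aim, hypothesis and endpoint address progression. If visit means V602 to V607 and data are complete, each test is also a comparison of different people, with about three times the SE of the within-person difference (1.27 against 0.41). The needed contrast can be estimated from the same MMRM, with SE between about 0.40 and 0.58 for 180 three-pair completers, or 0.70 and 1.00 for 60. These figures rest on the plan's ADAS-Cog13 inputs, no covariates, assumed completer counts and, for the lower ends, an assumed same-modality correlation up to 0.90. Without a margin, power to conclude no difference cannot be computed. The text should be corrected; the primary ICC does not depend on it.

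**What to change.** Keep the MMRM and change the text around it, in SAP 6.6 and Protocol 9.4.4 alike.

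1. State that visit means V602 to V607.
2. Replace the per-visit null with two contrasts: (a) the difference between modalities in same-modality change, V602 to V606 pooled with V603 to V607; (b) the modality difference averaged over the two visits of each pair, by pair and pooled over pairs.
3. Report both as estimates with 95% CIs.
4. Judge the no-difference hypothesis from the CI of (a) against a pre-stated margin, not from non-significance.
5. In Protocol 3, replace the V602 to V608 span with the visits used in (a).

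The cost is wording only, with no new data and no new model. A margin has to be chosen and justified. Contrast (a) will be imprecise if few participants complete Pair 3. Protocol 9.4.4 already limits the later-pair ICCs to description below 50 pairs, and the sponsor could extend that rule to (a).
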